1.0 INTRODUCTION

This statistical analysis plan provides details of the proposed statistical analyses for the clinical trial entitled “A Phase I/IIa Dose Escalation Safety Study of Subretinally Injected UshStat, Administered to Patients with Retinitis Pigmentosa Associated with Usher Syndrome Type 1B.” Study number TDU13600. This document contains a review of the study objectives and design, general statistical considerations, comprehensive statistical analysis methods for efficacy and safety endpoints, and a list of proposed tables and graphs. Any deviation from this statistical analysis plan will be described in the final study report, as appropriate.

2.0 STUDY OBJECTIVES

2.1 Primary Objective

To evaluate the safety and tolerability of ascending doses of subretinal injections of UshStat in patients with Usher syndrome type 1B.

2.2 Secondary Objective

To evaluate possible biological activity of UshStat.

3.0 STUDY DESIGN

This is a Phase I/IIa open-label dose escalation study of subretinally injected UshStat in patients with Usher’s retinitis pigmentosa (RP). All patients will be followed for 48 weeks. After 48 weeks, patients will enter an open-label safety study, and long-term follow-up visits, including ophthalmological examinations and recording of Adverse Events (AEs), will continue for 240 weeks (five years). For a subsequent 10 years, delayed AEs will also be monitored. Details of the assessments and analysis methods for this long-term follow-up study will be discussed in a separate SAP.

A projected total of up to 18 patients will be enrolled in this study, consisting of five dose cohorts. The study is separated into a dose escalation phase, Part A (Cohorts 1, 2 and 3), followed by two dose extension phases at the maximum tolerated dose (MTD), Parts B (Cohort 4) and C (Cohort 5). Part A will evaluate three ascending dose levels of UshStat in 300 μ L of vehicle. Up to nine patients will be enrolled in Part A, three patients per dose cohort. All patients enrolled in Part A must be at least 18 years of age, have clinical and molecular diagnosis of RP associated with Usher syndrome type 1B caused by *MYO7A* mutation(s), exhibit concentric constriction of kinetic visual field centrally in the worse seeing eye to \leq 20 degrees confirmed by visual field measurement by Semi-automated Kinetic Perimetry (SKP), and have no detectable rod-derived amplitudes on full-field electroretinogram (ERG).

In Part A of the study, a minimum interval of 21 days between the dosing of the first and subsequent patients in each cohort and a minimum interval of 28 days between cohorts has been selected in order for the DSMB to assess any acute toxicity, post-operative complications and the safety profile at each dose level of UshStat. The DSMB will be responsible for determining whether to proceed enrolling the next cohort of patients. Based on accrual of the data, the DSMB will comprehensively review the safety and tolerability of UshStat and make the decisions regarding dose escalation, study continuance, and recommended amendments to the protocol. If after a minimum interval of 28 days from the dosing of the third patient in a given cohort, the safety and tolerability is considered satisfactory by the DSMB, then the next cohort of three patients will be enrolled. The maximum tolerated dose (MTD) will be defined as the highest dose level that has an acceptable safety and tolerability and positive benefit/risk profile in the opinion of the DSMB.

If the safety and tolerability is considered satisfactory by the Data Safety and Monitoring Board (DSMB), regulatory authorities and institutional review boards (IRB) / independent ethics committees (EC) in Part A of the study, then the study will proceed to Part B that may enroll a maximum of three patients in parallel.

Patients enrolled in Part B must be at least 18 years old, have RP associated with Usher syndrome type 1B caused by *MYO7A* mutation(s), exhibit concentric constriction of kinetic visual field centrally in the worse seeing eye equating to a horizontal visual field diameter of >20 degrees confirmed by visual field measurement by Semi-automated Kinetic Perimetry (SKP), exhibit visual field loss in the worse seeing eye that is equivalent to at least 30% reduction from normal sensitivity volume (decibel-steradians) on full-field German Adaptive Thresholding Estimation (GATE) Static Perimetry using the size V test target, and have no detectable rod-derived amplitudes on full field ERG.

Part C provides the opportunity to extend the study to include pediatric patients at least six years of age. Prior to inclusion of pediatric patients, the DSMB will review all safety data three months after all three patients in Cohort 4 have been dosed. An interim report including all available safety data, preliminary efficacy/activity data and the recommendations from the DSMB will be submitted to regulatory agencies and institutional review boards/ethics committee for review before patients of at least six years of age will be included in Part C of the study (Cohort 5).

The UshStat doses to be studied are:

Subretinal Injection				
Part A				
Cohort	Age	Number of patients	Vector total dose per eye	Volume
1	≥ 18	3	1.4×10^5 TU	300 μ L
2	≥ 18	3	4.7×10^5 TU	300 μ L
3	≥ 18	3	1.4×10^6 TU	300 μ L

Part B				
4	≥ 18	3	MTD	300 μ L

Part C				
5	≥ 6	Up to 6	MTD	300 μ L

The initial UshStat dose to be studied will be 1.4×10^5 transducing units (TU), in 300 μ L of vehicle. Dose levels will increase to a maximum of 1.4×10^6 TU. The MTD will be defined as the highest dose level that has an acceptable safety and tolerability and positive benefit/risk profile in the opinion of the DSMB.

Patients will be allocated to active treatment (UshStat), in the order in which they are enrolled into the study. A minimum of 21 days must be allowed between dosing of the first and subsequent patients in any cohort, and a minimum of 28 days must be allowed between the final patient of one cohort and the first patient of the subsequent cohort. Three patients (with 21 days of follow-up between the first and subsequent patients) will be initially enrolled into the first cohort and receive the lowest dose of study drug (1.4×10^5 TU). If the DSMB agrees safety and tolerability are acceptable for this group of patients at the lowest dose (after a minimum of 28 days), then three more patients will be enrolled into the second cohort, receiving the next dose of UshStat (4.7×10^5 TU). Patients in Cohort 3 will receive a dose of 1.4×10^6 TU of investigational medicinal product (IMP), in accordance with the procedures outlined in the preceding paragraph.

Following determination of the MTD and review of the Part A study data by the DSMB and the appropriate regulatory authorities (IRB/EC), three patients will be enrolled in parallel at the MTD in Part B (Cohort 4). Finally, the DSMB will review all safety data three months after all three patients in Cohort 4 have been dosed, and regulatory agencies and IRB/EC will review an interim report including all available safety data, preliminary efficacy/activity data and the recommendations from the DSMB. Patients of at least six years of age will be included in Part C of the study (Cohort 5).

3.1 Study Stopping Criteria

The following are considered stopping criteria:

- Prolonged anterior chamber inflammation and/or prolonged posterior chamber inflammation continuing without signs of resolution 28 days after UshStat administration.

Criteria for suspending enrolment or further study conduct are defined in the DSMB Charter and all events will be reviewed by the DSMB. In the event of early study termination, all patients who have been dosed with UshStat will continue to be followed-up as per protocol. In addition, the study enrolment may be terminated at any time at the request of the Food and Drug Administration (FDA), the IRB/EC, the primary investigator (PI), or Sponsor.

3.2 Dose Limiting Toxicities

Dosing will stop if a dose-limiting toxicity is encountered in a dosing cohort. Events that constitute a dose-limiting toxicity are defined by the DSMB Charter. Dose-limiting toxicities include:

- Severe or persistent ocular inflammation;
- Other significant ocular toxicity (e.g., large retinal detachment, evidence of direct toxicity);
- Other systemic toxicities (e.g., acute allergic reaction);
- Any safety issue that has been identified that adversely changes the benefit/risk balance to study participants.

4.0 TARGETED STUDY POPULATION

Patients will be recruited from the hospitals' Usher syndrome type 1B patient population following IEC/IRB and regulatory approval. Up to 18 patients of either sex with Usher syndrome type 1B will be enrolled. This is a multicenter study with sites in the USA and EU. The selected sites have extensive experience in ophthalmic surgery, intraocular injections and handling of gene therapy products.

4.1 Inclusion Criteria

4.1.1 Main Inclusion Criteria

Patients must meet ALL of the following criteria to be considered for enrolment into this study.

1. Signed and dated written informed consent must be obtained from the patient (or assent in the case of minors from their legal guardian/representative), in accordance with the local regulations.
2. Clinical and molecular diagnosis of RP associated with Usher syndrome type 1B, caused by at least one pathogenic *MYO7A* mutation on both alleles, confirmed by direct sequencing and co-segregation analysis within the patient's family.

3. Patients must have suitable verbal/auditory and/or tactile sign language communication (in the opinion of the investigator) as to allow written informed consent to be obtained.
4. Females of childbearing potential must have a negative urine pregnancy test at screening and at baseline, and agree to use an effective form of contraception such as the contraceptive pill or intra uterine device for at least three months following UshStat administration, or be surgically sterile or postmenopausal, with the last menstrual period being over two years prior to enrollment.
5. Males of reproductive potential must agree with their partner to use two forms of contraception, including one barrier method for at least three months following UshStat administration if their partner is of childbearing capacity, or must be surgically sterile.

Partners of study patients should use barrier contraception for at least three months after UshStat administration.

4.1.2 Specific Inclusion Criteria for Cohorts 1, 2 and 3

- ≥ 18 years of age;
- Concentric constriction of kinetic visual field centrally in the worse seeing eye equating to a horizontal visual field diameter of ≤ 20 degrees, measured through the center of the visual field grid. The visual field constriction will be measured by Semi-automated Kinetic Perimetry (SKP) and the degrees of constriction will be confirmed by centralized independent assessment of the SKP data;
- No detectable rod-derived amplitudes on the full field electroretinogram performed to ISCEV standards.

4.1.3 Specific Inclusion Criteria for Cohort 4

- ≥ 18 years of age;
- Concentric constriction of kinetic visual field centrally in the worse seeing eye equating to a horizontal visual field diameter of > 20 degrees, measured through the center of the visual field grid. The visual field constriction will be measured by Semi-automated Kinetic Perimetry (SKP) and the degrees of constriction will be confirmed by centralized independent assessment of the SKP data;
- Visual field loss in the worse seeing eye that is equivalent to $\geq 30\%$ reduction from normal sensitivity volume (decibel-steradian) on full-field GATE Static Perimetry using the size V (1.7°) test target. The percentage reduction in normal sensitivity volume will be confirmed by centralized independent assessment of the data;
- No detectable rod-derived amplitudes on the full field electroretinogram performed to ISCEV standards.

4.1.4 Specific Inclusion Criteria for Cohort 5

- ≥ 6 years of age;
- Concentric constriction of kinetic visual field centrally in the worse seeing eye equating to a horizontal visual field diameter of >20 degrees, measured through the center of the visual field grid. The visual field constriction will be measured by Semi-automated Kinetic Perimetry (SKP) and the degrees of constriction will be confirmed by centralized independent assessment of the SKP data;
- Visual field loss in the worse seeing eye that is equivalent to $\geq 30\%$ reduction from normal sensitivity volume (decibel-steradian) on full-field GATE Static Perimetry using the size V (1.7°) test target. The percentage reduction in normal sensitivity volume will be confirmed by centralized independent assessment of the data;
- No detectable rod-derived amplitudes on the full field electroretinogram performed to ISCEV standards.

4.2 Exclusion Criteria

ANY one of the following criteria will exclude patients from being enrolled into the study:

1. Presence of significant ocular abnormalities in the study eye that in the opinion of the investigator would preclude the planned surgery, effective safety follow-up, or interfere with the interpretation of study endpoints (e.g. glaucoma, corneal or significant lens opacities, pre-existing uveitis, intraocular infection, choroidal neovascularization).
2. Any pre-existing factor or past history of eye disease in children that may predispose to an increased risk of surgical complications in the study eye (e.g. trauma, previous surgery, uveitis, congenital, developmental or structural abnormalities).
3. Concomitant systemic diseases including those in which the disease itself, or the treatment for the disease, can alter ocular function (e.g. malignancies, diabetes, juvenile rheumatoid arthritis or sickle-cell disease).
4. Any ocular surgery including laser and cataract surgery with intraocular lens implantation, aphakia or prior vitrectomy, in the study eye within six months of screening.
5. Any contraindication to pupil dilation in either eye.
6. Treatment with intravitreal, subtenon, or periocular steroid within four months of the screening visit.
7. Any known allergy to any component of the delivery vehicle or diagnostic agents used during the study (e.g. fluorescein, dilation drops), or medications planned for use during the peri-operative period, particularly topical, injected or systemic corticosteroids.
8. Life-threatening illness.

9. Alcohol or other substance abuse.
10. Laboratory test abnormalities or abnormalities in electrocardiogram or chest X-ray, that in the opinion of the principal investigator, are clinically significant and would make the patient unsuitable for participation in the study.
11. Intercurrent illness or infection 28 days prior to UshStat administration.
12. Contraindications to use of anesthesia (local or general, as appropriate).
13. Concurrent anti-retroviral therapy that would inactivate the investigational agent.
14. Pre-menopausal or non-surgically sterile women who are unwilling to use an effective form of contraception such as the contraceptive pill or intrauterine device.
15. Pregnant or breastfeeding women.
16. Males or females who do not agree to use barrier contraception as specified in the inclusion criteria.
17. History of any investigational agent within 28 days prior to UshStat administration.
18. Participation in a prior gene transfer therapy study.
19. Enrolment in any other clinical study, for any condition, including those relating to Usher syndrome type 1B, throughout the duration of the UshStat study.
20. Current or anticipated treatment with anticoagulant therapy or the use of anticoagulation therapy within the four weeks prior to surgery.
21. Long-term treatment with systemic corticosteroids within 28 days prior to the screening visit or ongoing systemic corticosteroid treatment at screening or on Day -1.
22. Current treatment with immunosuppressant therapies.
23. A history of malignancy within a five year period or have had a positive cancer screening test within a one year period of the screening visit.
24. Past medical history of HIV, or hepatitis A, B or C.
25. Inability to comply with the study protocol.

5.0 ENDPOINTS

5.1 Primary Endpoints

The primary objective of this study is evaluation of safety and tolerability of ascending doses of UshStat in patients with Usher syndrome type 1B. Safety and tolerability of the IMP will be evaluated using the following endpoints:

- The incidence of AEs over a 12-month period following a single intraocular dose of UshStat.
- Clinically important changes from baseline (Day -28) in the following safety assessments:
 - Best-corrected visual acuity (BCVA)
 - Slit-lamp examination
 - Indirect ophthalmoscopy
 - Fundus photography
 - Intraocular pressure (IOP)
 - Ocular coherence tomography (OCT)
 - Laboratory parameters
 - Vital signs
 - Concomitant medications
 - Physical examinations

For all primary endpoints with repeated measures, the primary time point will be considered the Week 48 (12-month) visit unless otherwise specified. BCVA and perimetry measurements are subject to broad intra-individual variability therefore the baseline value used for these measures will be an average of all the values obtained during the screening period.

5.2 Secondary Endpoints

The secondary objective is to evaluate UshStat for possible biological activity. An attempt will be made to determine a delay in retinal degeneration following subretinal injection of UshStat, through changes in function relative to the untreated contralateral eye using the following retinal analytical techniques:

- BCVA
- Indirect ophthalmoscopy
- Visual function questionnaire (VFQ-25)
- Full dilated slit-lamp examination
- Fundus photography – photomontage
- Visual field testing: Semi-automated Kinetic Perimetry (SKP), Full-Field GATE Static Perimetry, and microperimetry
- Autofluorescence

- Electroretinogram (ERG)
- OCT

The primary time points for secondary endpoints will be considered the Week 24 (6-month) and Week 48 (12-month) visits.

5.3 Other Endpoints

5.3.1 Immunology Endpoint

Humoral antibody response to UshStat administration.

5.3.2 Clinical Laboratory Tests

Hematology, biochemistry, urinalysis and other laboratory data will be measured at various time points throughout the study. Values will be flagged as High or Low if outside the laboratory normal range. Out-of-range values will be assessed as clinically significant (CS) or not clinically significant (NCS) by the investigator. CS out-of-range values will be recorded as adverse events. Blood for immunology and blood for PCR will also be taken at multiple time points throughout the study, as will urine samples for biodistribution assessment.

5.3.3 Biodistribution Endpoint

UshStat distribution in blood and urine will be assessed by polymerase chain reaction (PCR).

6.0 GENERAL STATISTICAL CONSIDERATIONS

6.1 Sample Size

This is an exploratory study for which the primary objective is to evaluate safety through adverse events and clinically meaningful impacts on vision endpoints. No formal sample size calculation has been performed. A total of 18 patients will be enrolled in five cohorts. The first three cohorts will consist of three patients each, and three and six patients will be enrolled in the fourth and fifth cohorts, respectively, at the MTD.

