4.12 RATIONALE FOR DOSING INTERVALS

A single unilateral dose of SAR421869 will be administered to each study patient who completes screening. Patients with advanced RP will be included in Cohorts 1, 2 and 3. Cohort 4 (MTD adults) and Cohort 5 (MTD including pediatric patients) will include patients with less advanced RP. In the non-clinical studies bleb resolution, vector clearance and gene expression have all occurred within two weeks post administration. Therefore, allowing 21 days between dosing individual patients (Cohorts 1-3) and 28 days between patient cohorts (Cohorts 1-4), will permit adequate time to assess short-term safety, including ocular inflammation and post-operative complications prior to dose escalation or the inclusion of adult patients with less advanced disease.

Thus, prior to dose escalation there will be up to 4 month safety data on the first patient, up to three months on the second and up to one month safety data on the third patient in the preceding cohort. These data will permit assessment of the short-term safety profile during the dose escalation part of the study. In addition, the long-term safety data (approximately 12-14 months) from patients with advanced disease dosed in the first three cohorts of the study will be available at the time of treating the final, less severely affected patient groups (Cohorts 4 and 5).

Prior to the inclusion of pediatric patients ≥ 6 years of age (Cohort 5), the DSMB will review all safety data, including data from Parts A and B, three months after all 6 patients in Cohort 4 have been dosed. An interim report including all available safety data, preliminary efficacy data and the recommendations from the DSMB will be submitted to the regulatory authorities and institutional review boards/ethics committees for review, before patients 6-17 years of age can be enrolled into Part C of the study.

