8 STUDY POPULATION

All patients must have a clinical and molecular diagnosis of RP caused by MYO7A mutations.

The results of the gene mutation analysis will be collected in the study database provided that written results are made available to the site, and participants (patients and/or the patient's parent[s]/legal guardian[s]) would give consent to record the results.

Twenty seven to 36 patients will complete the study. The protocol accommodates the possibility of several screen failures due to the rigorous inclusion and exclusion criteria.

Patients with differing disease severity and/or ages will be recruited, as defined by entry criteria.

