The purpose of this memorandum is to document that the Table of Contents for the final analysis for TDU13600 will differ from the Table of Contents in the currently approved version 2 of the SAP, dated 22JUL2016. The format of the tables will be the same as those in the SAP, except that the adverse event tables will be updated to the format used for the 23MAY2018 DSMB Report for SAR422459. The TOC and the adverse event table shells to be used for the final TLFs are included below.

Coordinating Center

Statistician Signature:

[figure not shown]
Date: 30AUG2019

Sponsor Statistician

Signature:

[figure not shown]
Date: 04SEP2019

Coordinating Center

Director Signature:

Date: 24SEP2019

TOC FOR ALL TLFs FOR TDU13600

- [Table 1A](#): Screening and Surgery Dates and Visit Completion by Cohort
- [Figure 1B](#): Patient Flow Diagram
- [Table 1C](#): Study Follow-up Completion and Withdrawal (including deaths)
- [Table 2A](#): Demographics Summary by Cohort
- [Listing 2B](#): Detailed Demographic Listing by Cohort
- [Listing 2C](#): General Medical History by Patient
- Listing 2D: Study Eye Ocular History by Patient
- Listing 2E: Fellow Eye Ocular History by Patient
- [Table 2F](#): Baseline Physical Examination Parameters by Cohort
- Table 2G: Reproductive Status by Patient
- Listing 2H: Detailed Surgery Listing by Patient
- Table 3A: Number and Percentage of Patients Experiencing TEAEs or No Events by Type of Event and Cohort
- Table 3B: Number of Patients Experiencing TEAEs by MedDRA SOC, HLGT, HLT, PT, and Cohort
- Table 3C: Number of Patients with TEAEs of Special Interest by MedDRA SOC, HLGT, HLT, PT, and Cohort
- Table 3D: Number of Patients with SAEs by MedDRA SOC, HLGT, HLT, PT, and Cohort
- Table 3E: Number of Patients Experiencing Inflammatory TEAEs by MedDRA SOC, HLGT, HLT, PT, and Cohort
- Table 3F: Number of Patients with TEAEs Related to IMP by MedDRA SOC, HLGT, HLT, PT, and Cohort
- Table 3G: Number of Patients with TEAEs Related to Procedure by MedDRA SOC, HLGT, HLT, PT, and Cohort
- [Table 3H](#): Listing of Adverse Events Prior to Treatment by Patient and Cohort
- [Table 3I](#): Listing of TEAEs by Patient and Cohort
- [Table 3J](#): Listing of Treatment Emergent Adverse Events of Special Interest by Patient and Cohort
- Table 3K: Listing of Treatment Emergent Serious Adverse Events by Patient and Cohort
- [Listing 3L](#): Ophthalmic Outcome Listing for Study Eye and Fellow Eye by Patient and Visit

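### SAP version 2 was not reconciled with protocol Amendment 8: total and cohort sizes, the Cohort 3 split, Cohort 4 and 5 eligibility and the pediatric-review passages differ

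*SAP*

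**What the plan says.** **Size.** SAP 6.1 states "A total of 18 patients will be enrolled in five cohorts" and breaks this down: "The first three cohorts will consist of three patients each, and three and six patients will be enrolled in the fourth and fifth cohorts". SAP 3.0 words the total as a ceiling: "A projected total of up to 18 patients will be enrolled in this study, consisting of five dose cohorts". SAP 4.0 also gives a ceiling of 18, and SAP 3.0 caps Part B at three. Protocol section 8 and the synopsis state "Twenty seven to 36 patients will complete the study". Protocol section 7 gives Part A at least 15 and up to 24 patients, and Cohort 4 six. The dosing tables in the synopsis and section 7 say up to six for Cohorts 4 and 5.

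**Review before pediatric enrolment.** SAP 3.0 places the DSMB review "three months after all three patients in Cohort 4 have been dosed". Protocol 4.12 places it "three months after all 6 patients in Cohort 4 have been dosed", and the synopsis and 4.14 agree. Protocol 7 and 9.1 refer to all Cohort 4 patients without a number. SAP 6.4 ties the interim data review to completion of Part B, also without a number.

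**Status of the SAP.** Amendment 8 carries approvals from August 2018. The memorandum of 30 August 2019 attached to the SAP says the final table of contents "will differ from the Table of Contents in the currently approved version 2 of the SAP, dated 22JUL2016". It replaces the table list and the adverse event shells and nothing else.

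**The concern.** The protocol leaves the detailed analysis to an SAP that is final before database lock. The SAP named as current predates Amendment 8 by two years and describes a different trial: fewer patients, an undivided Cohort 3, and other entry criteria for Cohorts 4 and 5. The sponsor reopened the SAP in 2019, a year after Amendment 8, and left these items as they were.

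Three things depend on them:

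- **Analysis set.** SAP 6.2 builds the primary data set from eligible patients, and SAP 4.1 supplies its own list of criteria.
- **Dose reporting.** The SAP shells stop at one Cohort 3 column, although the protocol now treats that cohort as several dose groups.
- **Pediatric review.** The two documents, and sections within each, describe the trigger for a major decision differently.

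**Working it through.** **Totals.** There is no power calculation to reproduce ("No formal sample size calculation has been performed"), so the check is to add the stated cohort sizes.

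- SAP: 3 + 3 + 3 + 3 + 6 = 18, as stated.
- Protocol, lower: 15 + 6 + 6 = 27, as stated.
- Protocol, upper: 24 + 6 + 6 = 36, as stated.

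Each document adds up, so this is a mismatch between documents and not an arithmetic slip. The difference is 27 − 18 = 9 to 36 − 18 = 18. Part A contributes 15 − 9 = 6 to 24 − 9 = 15, Cohort 4 contributes 6 − 3 = 3, and Cohort 5 contributes nothing.

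Two qualifications apply:

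- The SAP counts enrolments and the protocol counts completers. With the protocol's allowance of up to three replacements, enrolment could reach 27 + 3 = 30 to 36 + 3 = 39.
- The figure of 27 assumes a full Cohort 5, which is only up to six. Without Cohort 5 the minimum is 15 + 6 = 21.

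**Passages side by side.**

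| Item | SAP version 2 | Current protocol |
|---|---|---|
| Total | 18, or up to 18, enrolled (3.0, 4.0, 6.1) | 27 to 36 completing (synopsis, 8) |
| Part A | 9 (3.0) | 15 to 24 (synopsis, 7) |
| Cohort 3 | one group of 3 at 1.4×10^6 TU (3.0) | 3a, 3b, 3c; at least 9 patients (7) |
| Cohort 4 | at most 3 (3.0) | 6 (synopsis, 7); up to 6 (dosing tables) |
| Cohort 5 age | 6 or older, no upper limit (4.1.4) | 6-17 (8.2) |
| Field diameter, Cohorts 4-5 | above 20 degrees (4.1.3, 4.1.4) | 20 degrees or less (8.2) |
| No rod ERG response | all cohorts (4.1.2-4.1.4) | Cohorts 1, 2 and 3a only (8.2) |
| BCVA and ellipsoid-zone criteria | absent | Cohorts 3b, 3c, 4, 5 (8.2) |
| Pediatric review trigger | three Cohort 4 patients (3.0); end of Part B, no number (6.4) | all 6 (synopsis, 4.12, 4.14); all Cohort 4 patients (7, 9.1) |

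**Effect on the analysis set.** The two field criteria cannot both hold: a diameter of 20 degrees or less is never above 20. Every patient correctly enrolled in Cohort 4 or 5 under the protocol therefore fails SAP 4.1.3 or 4.1.4. Read literally, SAP 6.2 would exclude all of them. In Cohorts 3b and 3c the conflict is conditional: only a patient with a detectable rod response would meet the protocol and fail the SAP.

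**Effect on dose reporting.** Protocol Table 3 gives measured Cohort 3 doses of 0.33×10^6 and 2.4×10^6 (3a), 0.33×10^6 (3b) and 1.4×10^6 TU/eye (3c). The range is 2.4 / 0.33 = 7.3-fold, and all of it falls in the SAP's single Cohort 3 column.

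**Effect of the memorandum.** Its adverse event shell lists Cohorts 1 to 3 with three patients each: 3 + 3 + 3 = 9. That matches neither 18 nor 27 to 36. It also labels Cohort 3 as 1.4×10^6 TU, the target strength, although Table 3 gives that measured strength to none of the three 3a patients.

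**The case against.** The strongest reply is that the protocol, the DSMB, the regulators and the ethics committees govern enrolment, and the SAP's design section only restates an older design. The 2019 shell plans for nine patients in Cohorts 1 to 3, so Cohorts 4 and 5 may have no part in the final tables. This stands as a limit on practical effect. It does not remove the conflict, because nothing in the documents withdraws the 18-patient plan, the old criteria or the review trigger. It may also be said that eligible would in practice mean eligible under the protocol. That is likely, but the SAP prints its own criteria and does not say so.

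A reader might draw three stronger conclusions that the documents do not support:

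- **That a review prepared to the SAP would hold only half the required Cohort 4 patients.** SAP 6.4 sets the data review after completion of Part B and covers the first four cohorts, so it would include every Part B patient. The number three comes from the design section.
- **That the protocol's condition can never be met if fewer than six are enrolled.** Protocol 7 and 9.1 already refer to all Cohort 4 patients. The defect is uneven wording.
- **That the evidence before treating children can be sized from Cohort 4 alone.** With zero events the one-sided 95% upper bound would be 1 − 0.05^(1/3) = 63% for three patients and 1 − 0.05^(1/6) = 39% for six. But both documents have the DSMB review all safety data: 9 + 3 = 12 adults under the SAP and 15 + 6 = 21 to 24 + 6 = 30 under the protocol. Zero events is also hypothetical, since the amendment rationale reports a serious uveitis case in this study.

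Nor was the ERG criterion dropped altogether; it stays for Cohorts 1, 2 and 3a.

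**Conclusion.** The concern holds as a failure to reconcile the SAP with the current protocol. It is more than clerical, because it touches the stated size, the definition of the primary data set, the dose groups and a decision trigger. The totals differ by 9 to 18 patients, with the caveat that one counts enrolments and the other completers. Cohort 4 differs by three, and the field criteria for Cohorts 4 and 5 exclude each other. Power is not at issue, since neither document claims a sample size calculation.

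The conclusion assumes that the memorandum is right to call version 2 the current SAP and that no later SAP exists outside the documents supplied. The practical effect is small if Cohorts 4 and 5 are not part of the final analysis, as the nine-patient shell suggests. No text says this outright. Which pediatric-review trigger is right is not judged here.

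**What to change.** Before database lock, revise the SAP to match the current protocol on:

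- the total and cohort sizes, stating for each figure whether it counts enrolments or completers;
- the 3a, 3b and 3c reporting groups, with measured dose shown, since 3a itself contains two measured doses;
- eligibility by cohort and the Cohort 5 age range. Protocol 4.9 describes Parts B and C as having much less restricted fields, so the sponsor should confirm the field criterion before carrying it across.

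State whether Cohorts 4 and 5 remain in the final analysis, and bring the table shells into line with that statement. The sponsor and DSMB should reconcile the pediatric-review passages within the protocol (synopsis, 4.12, 4.14, 7, 9.1 and the dosing tables), within the SAP (3.0 and 6.4) and between the two documents.

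The cost is a document revision. No new data are needed.
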